5.1 Inclusion criteria

Participants eligible for inclusion in this study must meet **all** of the following criteria:

1. Signed informed consent must be obtained prior to performing any screening procedure.
2. Male or female ≥ 18 years of age at time of informed consent.
3. Histologically or cytologically confirmed diagnosis of Stage IV NSCLC (according to AJCC 8th edition) that is *BRAF* V600E mutation-positive by local test result from a qualified assay (NMPA and/or MOH-approved).
 - An archival or new tumor tissue sample should be available at the time of enrollment for central testing of *BRAF* V600E status (see [Section 8.5.3](#) for details).
4. Previously treated or untreated for metastatic NSCLC (prior systemic treatment in the adjuvant setting is allowed)
 - Participants previously treated should have received no more than 3 prior systemic therapies for metastatic disease, with at least one prior platinum based chemotherapy, and should have documented disease progression on a prior treatment regimen (i.e. RECIST 1.1)
 - Participants who have received prior therapy with checkpoint inhibitor therapy (i.e. anti-PD-1/PD-L1) as the last treatment regimen must have had confirmed disease progression (i.e. RECIST 1.1) while on or after this therapy prior to enrollment.
 - Participants with EGFR or ALK mutation who have previously received therapy with EGFR or ALK inhibitor(s) respectively are eligible.
5. Measurable disease per RECIST 1.1.
6. Anticipated life expectancy of at least 3 months.
7. ECOG performance status ≤ 2 .
8. Adequate bone marrow and organ function as defined by the following laboratory values without continuous supportive treatment (such as blood transfusion, coagulation factors and/or platelet infusion, or red/white blood cell growth factor administration) as assessed by local laboratory for eligibility:

Hematological

- Hemoglobin ≥ 9 g/dL
- Absolute neutrophil count $\geq 1.5 \times 10^9/L$
- Platelets $\geq 100 \times 10^9/L$

Coagulation

- PT/INR and PTT $\leq 1.5 \times$ ULN. Participants receiving anticoagulation treatment may be allowed to participate with INR established within the therapeutic range prior to enrollment.

Renal

- Serum creatinine $< 1.5 \text{ mg/dL}$

Hepatic

- Total bilirubin $\leq 1.5 \times$ ULN (upper limit of normal) except for participants with Gilbert's syndrome who may only be included if the total bilirubin is $\leq 3.0 \times$ ULN or direct bilirubin $\leq 1.5 \times$ ULN

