6.2 Other treatment(s)

6.2.1 Concomitant therapy

The investigator must instruct the participant to notify the study site of any new medication(s) he/she takes after start of study participation.

Prior antineoplastic therapies including medications, radiotherapy, and surgery are to be recorded on the separate prior antineoplastic therapy Case Report Forms during screening.

All medications, procedures, and significant non-drug therapies (including physical therapy, herbal/natural medications and blood transfusions) administered after the participant was enrolled into the study must be recorded on the appropriate Case Report Forms. Medication entries must be specific to trade name, dose and units, frequency and route of administration, start and discontinuation dates, and reason for therapy. For medications administered one time, the frequency column may reflect “once.”

Each concomitant drug must be individually assessed against all exclusion criteria/prohibited medication. If in doubt, the investigator should contact the Novartis medical monitor before

allowing a new medication to be started. If the participant is already enrolled, contact Novartis to determine if the participant should continue participation in the study.

In general, concomitant medications and therapies deemed necessary for the supportive care (e.g., such as anti-emetics, anti-diarrhea) and safety of the participant are allowed except those prohibited in [Section 6.2.2](#). Participants are permitted to use the following medications during study treatment:

- Limited-field palliative radiotherapy to non-target lesion(s) may be allowed after documented discussion with Novartis study physician as concomitant therapy such as local therapies administered during the study treatment. Any radiotherapy must be listed on the appropriate eCRF. In case of palliative radiotherapy, the participant should interrupt dabrafenib and trametinib for fractionated radiotherapy and stereotactic radiosurgery before and after radiotherapy as outlined below ([Anker et al 2016](#)).
 - Interrupt dabrafenib and trametinib \geq 3 days before and after fractionated radiation
 - Interrupt dabrafenib and trametinib \geq 1 day before and after stereotactic radiosurgery (SRS)
- Antivirus medications to manage HBV or HCV infection and/or prevent reactivation (e.g., tenofovir); supportive care.
- Medications to prevent or treat nausea or vomiting.

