6.5 Dose escalation and dose modification

6.5.1 Dose modifications

General guidelines regarding management and dose reduction for adverse events that are considered by the investigator to be related to study treatment and for which specific guidelines do not apply are provided in [Table 6-2](#). These guidelines are intended primarily for toxicities not easily managed with routine supportive care. For example, alopecia is not an indication for dose modification, nor is grade 2 nausea and vomiting that can be easily managed with anti-emetics.

The following section(s) address the specific instructions for mandatory dose modifications and recommended management for AEs considered suspected to be related to study treatment. For participants who do not tolerate the protocol-specified dosing schedule, dose interruptions or modifications are mandated in order to allow participants to continue study treatment.

If treatment related toxicities occur when dabrafenib and trametinib are used in combination, then both treatments should be simultaneously dose reduced, interrupted or discontinued with the exceptions shown below:

Exception where dose modification is necessary for only dabrafenib:

- Uveitis ([Table 6-14](#))

Exception where dose modifications are necessary for only trametinib:

- Retinal vein occlusions (RVO) ([Table 6-14](#)) and retinal pigment epithelial detachment (RPED) ([Table 6-15](#))
- Left ventricular ejection fraction (LVEF) reduction ([Table 6-13](#))
- Pneumonitis and ILD ([Table 6-10](#))

Table 6-2 Dose Modification Guidelines - General

Grade	Recommended adverse event management guidelines	Mandatory dose modification requirements
Grade 1 or Grade 2 tolerable	
• Monitor closely• Provide supportive care according to institutional standards	
• Continue dabrafenib and trametinib at the same dose level.
Grade 2 (intolerable) or Grade 3	
• Monitor closely.• Provide supportive care according to institutional standards	
• Interrupt dabrafenib and trametinib• When toxicity resolves to ≤ Grade 1 or baseline, restart dabrafenib and trametinib

Grade	Recommended adverse event management guidelines	Mandatory dose modification requirements

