6.5.2.6 Guidelines for Pneumonitis

Pneumonitis has been observed in participants receiving trametinib. To reduce the risk of pneumonitis, participants will be monitored closely for symptoms, evaluated with imaging and functional tests. Dose modification and supportive care guidelines for pneumonitis are described in [Table 6-10](#).

Table 6-10 Management and Dose Modification Guidelines for Pneumonitis

Pneumonitis (NCI-CTCAE v4.03)		
Grade	Adverse Event Management	Mandatory dose modification requirements
Grade 1	
 CT scan (high-resolution with lung windows) recommended Clinical evaluation and laboratory work-up for infection Monitoring of oxygenation via pulse-oximetry recommended Consultation of pulmonologist recommended 	
 Continue dabrafenib and trametinib at current dose
Grade 2	
 CT scan (high-resolution with lung windows) Clinical evaluation and laboratory work-up for infection Consult pulmonologist Bronchoscopy with biopsy and/or BAL recommended Symptomatic therapy including corticosteroids if clinically indicated 	
 Interrupt trametinib until toxicity recovers to \leq Grade 1 or baseline. Dabrafenib may continue 
 Once recovered, restart trametinib at the next lower dose level. Escalation to previous dose level after 4 weeks possible and consultation with Medical Lead

Pneumonitis (NCI-CTCAE v4.03)		
Grade	Adverse Event Management	Mandatory dose modification requirements
		
 • If no recovery to grade \leq 1 within 4 weeks, permanently discontinue trametinib. Dabrafenib may continue
Grade 3	
 • CT scan (high-resolution with lung windows) • Clinical evaluation and laboratory work-up for infection • Consult pulmonologist • Bronchoscopy with biopsy and/or BAL if possible • Symptomatic therapy including corticosteroids as clinically indicated • Oxygen indicated 	
 • Interrupt trametinib until toxicity recovers to \leq Grade 1 or baseline. Dabrafenib may continue • Once recovered, restart trametinib at the next lower dose level after consultation with medical lead. • Escalation to previous dose level after 4 weeks and consultation with Medical Lead is possible • If no recovery to grade \leq 1 within 4 weeks, permanently discontinue trametinib. Dabrafenib may continue

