6.5.2.7 Guidelines for Renal Insufficiency

Cases of renal insufficiency have occurred in participants receiving dabrafenib and the combination of dabrafenib and trametinib. Prior to start of study treatment, concomitant medications should be reviewed for the potential risk of inducing nephrotoxicity and concomitant medications should be modified if clinically possible. Management and dose modifications guidelines are provided in [Section 6.2](#). Close monitoring of serum creatinine, treatment associated pyrexia (see [Table 6-5](#)), and treatment interruption for increased serum creatinine > 2 mg/dL (or > 0.5 mg/dL above baseline). Nephrology consultation should also be obtained in absence of obvious cause for persistent creatinine elevation (e.g volume depletion).

Table 6-11 Mandatory dose modifications and recommended clinical management guidelines for renal insufficiency

Acute kidney injury (NCI-CTCAE v4.03)		
Grade	Recommended adverse event management guidelines	Mandatory dose modification requirements
Grade 1 (Creatinine level increase of >0.3 mg/dL; creatinine 1.5 - 2.0 x above baseline)	
 • If the increase in creatinine is confirmed: 
 a. Assess fluid status and consider fluid bolus b. Monitor serum creatinine at least every 2 days until back to baseline 	
 • If the increase in creatinine is confirmed: 
 a. Interrupt dabrafenib and trametinib • If creatinine returns to baseline:

Acute kidney injury (NCI-CTCAE v4.03)		
Grade	Recommended adverse event management guidelines	Mandatory dose modification requirements
	
 c. If creatinine returns to baseline: 
 a. resume routine creatinine monitoring per protocol • Promote hydration and cessation of nephrotoxic drugs 	
a. Continue dabrafenib and trametinib at the same dose.

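### Protocol 6.5.2.7 gives two different creatinine triggers for interrupting study treatment, one in the prose and one in mandatory Table 6-11, and points to a section with no renal dose rules

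*Protocol*

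**What the plan says.** Protocol 6.5.2.7 (Guidelines for Renal Insufficiency) states the interruption rule twice.

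- **Prose.** Among the monitoring measures it lists "treatment interruption for increased serum creatinine > 2 mg/dL (or > 0.5 mg/dL above baseline"). It does not ask for a repeat value first.
- **Table 6-11, titled as mandatory dose modifications.** The lowest row is "Grade 1 (Creatinine level increase of >0.3 mg/dL; creatinine 1.5 - 2.0 x above baseline"). Its mandatory column interrupts dabrafenib and trametinib under the condition "If the increase in creatinine is confirmed". From Grade 2 (2 to 3 times baseline) upward, interruption carries no confirmation condition.

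Section 6.5.1 introduces these rules as "mandatory dose modifications and recommended management for AEs considered suspected to be related to study treatment". Section 6.5.1.1 allows no deviation from mandatory interruptions.

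For the dose rules the prose says "Management and dose modifications guidelines are provided in" Section 6.2. That section covers concomitant, cautioned and prohibited therapy. Its only instruction to interrupt study drug concerns palliative radiotherapy. The neighbouring Section 6.5.2.6 names its own table: "Dose modification and supportive care guidelines for pneumonitis are described in" Table 6-10.

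**The concern.** A site cannot satisfy both texts by following only one. A site working from the prose figure would keep dosing through rises that the table treats as a mandatory hold. A site working from the table would wait for a repeat sample where the prose holds at once, and the section sets no deadline for that repeat.

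The rule is used often, because creatinine is in the chemistry panel scheduled at every treatment visit (Protocol Tables 8-1 and 8-5). Section 6.5.2.7 itself reports renal insufficiency with dabrafenib and with the combination, and pre-renal and intrinsic renal failure is a listed adverse event of special interest (Protocol 10.1.1). Participant safety comes first. Second, dose interruptions and their reasons are tabulated (Protocol 12.3, SAP 2.4.1), and those tables would mix two practices if sites applied the rule differently.

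**Working it through.** The plan offers no figure to reproduce, so the check sets the two rules side by side.

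**Inputs**

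- Baseline creatinine *b* is below 1.5 mg/dL (Protocol 5.1, inclusion criterion 8). Assumption: the baseline for these rules is the entry value.
- Prose trigger: value above 2 mg/dL, or above *b* + 0.5.
- Table Grade 1: rise above 0.3 mg/dL; 1.5 to 2.0 times baseline. Assumption: the phrase about times above baseline means a multiple of baseline.
- Table Grade 2 starts at 2*b*.

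**Step 1: the operative prose trigger.** Since *b* < 1.5, *b* + 0.5 < 2.0. Any value above 2 mg/dL is therefore already more than 0.5 above baseline, and the prose rule reduces to *b* + 0.5.

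**Step 2: where the table starts.** With the semicolon read as 'or', Grade 1 starts at min(*b* + 0.3, 1.5*b*), which is *b* + 0.3 for *b* ≥ 0.6.

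**Step 3: two bands of disagreement (mg/dL, 'or' reading)**

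| Baseline | Table starts | Prose starts | Grade 2 starts (2*b*) | Table only | Both, but table waits for confirmation |
|---|---|---|---|---|---|
| 0.6 | 0.9 | 1.1 | 1.2 | 0.9–1.1 | 1.1–1.2 |
| 0.8 | 1.1 | 1.3 | 1.6 | 1.1–1.3 | 1.3–1.6 |
| 1.0 | 1.3 | 1.5 | 2.0 | 1.3–1.5 | 1.5–2.0 |
| 1.2 | 1.5 | 1.7 | 2.4 | 1.5–1.7 | 1.7–2.4 |
| 1.4 | 1.7 | 1.9 | 2.8 | 1.7–1.9 | 1.9–2.8 |

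The table-only band is 0.5 − 0.3 = 0.2 mg/dL wide at each of these baselines. The second band exists whenever *b* + 0.5 < 2*b*, that is, *b* > 0.5.

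**Step 4: cases that do not depend on the semicolon**

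- 0.8 to 1.2: rise 0.4, ratio 1.2/0.8 = 1.50. This is Grade 1 under 'or' and under 'and', so the table interrupts once confirmed. The rise is not above 0.5 and the value is not above 2, so the prose does not interrupt.
- 1.0 to 1.6: rise 0.6, ratio 1.60. This is Grade 1 on either reading. The prose interrupts at once; the table interrupts after confirmation.

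**Step 5: the semicolon.** Read as 'and', a rise from 1.4 to 2.0 (0.6; 2.0/1.4 = 1.43) meets the prose but no row of the table. Read as 'or', every rise above 0.5 is also above 0.3, so no value that meets the prose falls outside the table. The protocol's usage favours 'or'. Table 6-9 separates stool count and ostomy output by semicolons within a grade, and these must be alternatives because most patients have no ostomy.

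**The case against.** The strongest reply is that the documents already say which text wins. Table 6-11 sits in the same section, is titled mandatory, and Section 6.5.1.1 bars deviations. The prose is a sentence fragment with no 'must'. It never tells a site to keep dosing below +0.5, so it can be read as a sufficient condition rather than the only one. On the 'or' reading, a site that follows the table meets both texts apart from timing. This stands as a reason to rate the practical risk low. It does not remove the contradiction: precedence favours the table, yet the table is the slower rule for an unconfirmed Grade 1 rise above 0.5 mg/dL.

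The two texts could also be combined as an immediate hold above +0.5 and a hold after confirmation below it. That is coherent, and the fix adopts it, but neither text says so.

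On the pointer, the reader is already in the renal section with the table at hand. Table 6-4 has a row for renal function alterations, although its guideline links are not readable in the text supplied. A reader might infer that sites could not find the renal rules. The documents do not support that; the reference is simply wrong.

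**Conclusion.** The point holds as a minor inconsistency in a safety rule that is wrong as written. Under the stated assumptions on baseline and on multiples of it, the triggers differ by 0.2 mg/dL at baselines of 0.6 to 1.4 mg/dL, and they differ on confirmation for rises above 0.5 mg/dL that remain Grade 1. The example of 0.8 to 1.2 mg/dL needs no choice about the semicolon.

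Three stronger conclusions are tempting and not supported:

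- **That the table is simply the stricter rule at every baseline.** This is true of the threshold on the 'or' reading, but it ignores that the prose acts without confirmation.
- **That the prose is the stricter threshold above a baseline of 1.0 mg/dL.** This needs the 'and' reading (1.5*b* > *b* + 0.5 when *b* > 1.0), which is strained given Table 6-9.
- **That participants were mis-dosed or efficacy results are compromised.** The documents give no frequency for such rises and no record of how sites acted, and the ORR analysis does not use these thresholds.

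**What to change.** Make three wording changes together in Protocol 6.5.2.7:

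1. Change the pointer from Section 6.2 to Table 6-11.
2. Write the Grade 1 definition as: *>0.3 mg/dL above baseline OR 1.5–2.0 × baseline*.
3. Replace the prose threshold with: *Interrupt per Table 6-11; for creatinine >2 mg/dL or >0.5 mg/dL above baseline, interrupt at once without waiting for confirmation.*

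Deleting the prose threshold outright would be the wrong repair, because it would delay the hold for unconfirmed Grade 1 rises above 0.5 mg/dL. Change 2 belongs in the set because deferring to the table under an 'and' reading would leave a case such as 1.4 to 2.0 mg/dL outside every row. The restart rules stay as they are.

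The cost is a few lines in one section, with no new data, visits or analyses. Section 14.1 requires a written amendment for protocol changes; a clarification letter could meanwhile remind sites that Table 6-11 binds. The SAP's last update is dated 15-Oct-2024, before final database lock, so the change may come late: it affects dosing only while participants remain on treatment.

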6.5.2.10 Guideline dose modification and management for hemophagocytic lymphohistiocytosis (HLH)

In post marketing experience, hemophagocytic lymphohistiocytosis (HLH) has been observed with dabrafenib and trametinib combination therapy. Since post-marketing adverse drug reactions are reported from a population of uncertain size, the exact frequency of HLH in patients receiving dabrafenib and trametinib is unknown. HLH is a rare, life-threatening condition caused by an overactive, abnormal response of the immune system ([Kikuchi et al 2022](#)), HLH is associated with a constellation of multiple clinical and laboratory features that may include fever, hepatosplenomegaly, hypertriglyceridemia, hypofibrinogenemia, high serum ferritin, multilineage cytopenias and hemophagocytosis. If HLH is suspected, treatment

should be interrupted. If HLH is confirmed, treatment should be permanently discontinued and appropriate management of HLH per institutional standards should be initiated.

6.5.2.11 Mandatory dose modification and management guideline for visual changes

Episodes of visual changes have been observed in participants receiving trametinib, dabrafenib or the combination of dabrafenib/trametinib. An ophthalmologist should be consulted if changes in vision develop. However, if the visual changes are clearly unrelated to study treatment (e.g., allergic conjunctivitis), then monitor closely as it may be reasonable to defer ophthalmic examination.

Treatment with dabrafenib has been associated with the development of uveitis, including iritis. Monitor participants for visual signs and symptoms (such as, change in vision, photophobia and eye pain) during therapy. Permanently discontinue dabrafenib for persistent \geq Grade 2 uveitis (including iritis and iridocyclitis) of > 6 weeks duration. No dose modification of trametinib is required when taken in combination with dabrafenib.

In participants treated with trametinib, special attention should be given to retinal findings (e.g., RPED) or retinovascular abnormalities (i.e., branch or central RVO). Retinopathy is a known adverse drug reaction seen with MEK inhibitor therapy, including trametinib. MEK inhibitor associated serous retinopathy typically manifests bilaterally within days of treatment initiation with a median time to onset of one month (Cruz-Merino et al 2017, Francis et al 2017). Treatment emergent cases of RVO and RPED should be reported as SAEs.

Guidelines for dose modification and management for visual changes and/or ophthalmic examination findings considered to be related to dabrafenib and/or trametinib are provided in [Table 6-14](#) and [Table 6-15](#).

Table 6-14 Mandatory dose modification and recommended clinical management for visual changes and/or ophthalmic examination findings

Visual changes (Eye disorders – Other, CTCAE Version 4.03)		
Grade	Recommended adverse event management guidelines	Mandatory dose modification requirements
Grade 1 ^a	Consult ophthalmologist within 7 days of onset	
• If dilated fundus examination cannot be performed within 7 days of onset, interrupt trametinib until RPED and RVO can be excluded by retina specialist/ophthalmologist. Continue dabrafenib.• If RPED and RVO excluded, continue (or restart) trametinib at the same dose level.• If RPED suspected or diagnosed: see RPED dose modification in Table 6-15; report as SAE if diagnosed.• If RVO diagnosed: Permanently discontinue trametinib and report as SAE.
Grade 2 and Grade 3	Consult ophthalmologist immediately	
• Interrupt trametinib. Dabrafenib may be continued at the same dose ^b. If RPED and RVO excluded, restart trametinib at the same dose level.• If RPED diagnosed, see RPED dose modification in Table 6-15; report as SAE.

Visual changes (Eye disorders – Other, CTCAE Version 4.03)		
Grade	Recommended adverse event management guidelines	Mandatory dose modification requirements
		
 If RVO diagnosed: Permanently discontinue trametinib and report as SAE.
Grade 4	Consult ophthalmologist immediately	
 Interrupt trametinib. Dabrafenib may be continued at the same dose ^b. If RPED and RVO excluded, should consider restarting trametinib at same or reduced dose after discussion with study medical monitor. If RVO or RPED diagnosed, permanently discontinue trametinib and report as SAE.
^a If visual changes are clearly unrelated to study treatment (e.g., allergic conjunctivitis), monitor closely but ophthalmic examination is not required.		
^b Permanently discontinue dabrafenib for \geq Grade 2 uveitis (including iritis and iridocyclitis) of > 6 weeks duration.		

Table 6-15 Mandatory dose modification and recommended clinical management for retinal pigment epithelial detachments (RPED) suspected to be related to trametinib treatment

Retinal pigment epithelial detachments (RPED)		
Grade	Recommended adverse event management guidelines	Mandatory dose modification requirements

 Grade 1 (Asymptomatic; clinical or diagnostic observations only) 	
 If RPED worsens follow instructions below. 	
 Continue dabrafenib and trametinib with retinal evaluation monthly until resolution.

 Grade 2-3 RPED (Symptomatic with mild to moderate decrease in visual acuity). 	
 Retinal evaluation monthly. 	
 Interrupt trametinib and continue dabrafenib. If improved to \leq Grade 1, restart trametinib at next lower level If not improved to \leq Grade 1 within 3 weeks, permanently discontinue trametinib

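### For diagnosed uveitis, Protocol Sections 6.5.1 and 6.5.2.11 call for no change to trametinib, but the Grade 2–4 cells of Table 6-14 interrupt it without exempting uveitis

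*Protocol*

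**What the plan says.** Protocol Section 6.5.1 sets a general rule for treatment-related toxicity under the combination: "then both treatments should be simultaneously dose reduced, interrupted or discontinued with the exceptions shown below". The first exception is introduced by "Exception where dose modification is necessary for only dabrafenib". Its only entry is uveitis, with a pointer to Table 6-14.

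Section 6.5.2.11 has a paragraph on uveitis. It requires permanent discontinuation of dabrafenib for persistent uveitis of at least Grade 2 lasting more than 6 weeks, and ends: "No dose modification of trametinib is required when taken in combination with dabrafenib".

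The same section introduces Tables 6-14 and 6-15 as "Guidelines for dose modification and management for visual changes and/or ophthalmic examination findings considered to be related to dabrafenib and/or trametinib". Table 6-14 is organised by grade of visual change and has no row for uveitis. In its mandatory column:

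- Grade 2 and Grade 3: "Interrupt trametinib. Dabrafenib may be continued at the same dose ^b. If RPED and RVO excluded, restart trametinib at the same dose level".
- Grade 4: the same opening instruction, "Interrupt trametinib. Dabrafenib may be continued at the same dose". If RPED and RVO are excluded, the site "should consider restarting trametinib at same or reduced dose after discussion with study medical monitor".
- Footnote b, attached to both cells, repeats the threshold for permanently stopping dabrafenib: "Grade 2 uveitis (including iritis and iridocyclitis) of > 6 weeks duration", at that grade or higher.

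Section 6.5.1.1 allows no deviation from mandatory interruptions or reductions.

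**The concern.** A site with a participant who has uveitis is sent by Section 6.5.1 to Table 6-14, expecting a rule that touches dabrafenib only. For Grade 2 to 4 events it finds a mandatory interruption of trametinib, and nothing that exempts a diagnosed uveitis. The text of Section 6.5.2.11 says that no such step is needed.

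These rules are labelled mandatory and deviations are barred, so sites need a single answer. As written, one site may interrupt trametinib and another may not, for the same event, and each can point to the protocol. Uveitis is a listed adverse event of special interest in both documents. Interruptions, reductions and their reasons are tabulated, and exposure and dose intensity are reported for each drug (SAP Section 2.4.1). Inconsistent handling would therefore appear in the reported trametinib dosing.

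**Working it through.** No figure in the plan depends on this point, so the check is a comparison of the text.

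**Does modification include interruption?** Yes. The general rule in Section 6.5.1 covers reduction, interruption and discontinuation, and the exceptions are exceptions to that rule. Protocol Section 12.3 likewise counts interruptions as dose adjustments.

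**Is uveitis within Table 6-14?** The title (visual changes; Eye disorders – Other) does not settle it, but four places bring uveitis in. Section 6.5.1 points to the table by number for uveitis. Table 6-4 puts uveitis in the visual-changes row, under dabrafenib. The lead-in to the tables covers findings related to either drug. Footnote b names uveitis in the Grade 2–3 and Grade 4 cells.

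**Side by side:**

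| | Sections 6.5.1 and 6.5.2.11, uveitis | Table 6-14, Grade 2–3 | Table 6-14, Grade 4 | Agree? |
|---|---|---|---|---|
| Trametinib, first action | No modification needed | Interrupt | Interrupt | No |
| Trametinib, RPED and RVO excluded | No modification needed | Restart at same dose | Consider restart, same or reduced dose, after discussion with the medical monitor | Grade 2–3: only once the hold has ended. Grade 4: no |
| Dabrafenib | Stop permanently if Grade 2 or higher for more than 6 weeks | May continue, subject to footnote b (same threshold) | May continue, subject to footnote b (same threshold) | Yes |

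The Grade 1 row lies outside the point. It holds trametinib only if a dilated fundus examination cannot be done within 7 days, and it does not carry footnote b.

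**Is there an exemption elsewhere?** None was found. No section says that the trametinib instruction lapses, or does not start, once uveitis is the diagnosis.

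**How many participants?** The documents give no uveitis rate. Assuming 1% to 5% of the planned 40:

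- 0.01 × 40 = 0.4
- 0.05 × 40 = 2

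That is roughly 0 to 2 participants over all grades. Grade 4 cases, where the conflict is clearest, would be a subset whose size cannot be derived from the documents.

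**The case against.** The strongest reply is that the passages can be read in sequence. Table 6-14 deals with visual changes of any cause, and its trametinib branches turn on RPED and RVO, which Section 6.5.1 lists as trametinib-only exceptions. On that reading, trametinib is held while retinal causes are excluded, and the uveitis paragraph governs once uveitis is the diagnosis.

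Much of this stands for Grade 2–3, where the table itself restarts trametinib at the same dose. It does not clear the point. A hold is still an interruption. The Grade 1 row ties its hold explicitly to excluding RPED and RVO, while the higher-grade cells order the interruption outright. The sequential reading is also nowhere written down. At Grade 4 it fails on the table's own terms, because excluding both conditions leads only to considering a restart, perhaps at a lower dose.

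Three stronger readings are tempting, and the documents do not support them:

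- **That the table reverses the text.** It does not for dabrafenib: footnote b carries the same grade and duration threshold as Section 6.5.2.11. Nor does either place tell sites to hold dabrafenib for uveitis, so one site holding one drug while another holds the other does not follow from the text.
- **That a site cannot comply with both.** Section 6.5.2.11 says that modification is not required; it does not forbid it. A site that follows the table breaches neither passage.
- **That the hold is open-ended at every grade.** The Grade 2–3 cell says when trametinib restarts and at what dose.

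**Conclusion.** The point holds as an unresolved inconsistency about trametinib in diagnosed uveitis. It is clear at Grade 4 and weaker at Grade 2–3, where reading the interruption as a diagnostic hold is fair but unstated. The dabrafenib rule is consistent and needs no change.

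The likely effect is small: about 0 to 2 of 40 participants, under an assumed rate of 1–5% that has no source in the documents. The ORR definition and analysis do not depend on it. What could be affected is consistency of dosing between sites and, through it, the descriptive trametinib interruption, reduction and dose-intensity summaries. It should still be corrected, because the rules are mandatory, deviations are not allowed, and the event concerns the eye. The conclusion rests on uveitis falling within Table 6-14, which the pointer in Section 6.5.1 and footnote b both indicate.

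**What to change.** Reconcile Protocol Sections 6.5.1 and 6.5.2.11 with Table 6-14. Either add a uveitis row to the table or add one sentence to Section 6.5.2.11. It should state, for diagnosed uveitis, whether the trametinib interruption in the Grade 2–3 and Grade 4 cells applies, and whether the Grade 4 restart provision applies, in each case including after RPED and RVO have been excluded. Which rule to adopt is for the sponsor's clinical team, and this review takes no view on it.

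The cost is protocol wording only, handled through the amendment process in Section 14.1. No assessment, data item or analysis changes.
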